### 1.2 *Study Aim*

This study will evaluate the accuracy and performance of the prototype device compared to commercial tympanometer in pediatric and adult population.

### 1.3 *Research Objectives and Study Hypotheses*

**Objective 1 (primary):**

To obtain preliminary estimates of the accuracy of the prototype device compared to commercial tympanometer based on audiologist's interpretation (for both devices).

**Hypothesis 1:**

The diagnostic accuracy (sensitivity and specificity) of the prototype device based on audiologist's interpretation as compared to the commercial tympanometer based on audiologist's interpretation is 80% or greater.

**Objective 2 (primary):**

To compare categorical classifications of tympanogram types (A, B, C) based on audiologist's interpretation compared to the machine learning algorithm's interpretation.

**Objective 2A:**

To obtain preliminary estimates of the agreement between audiologist's interpretation of the prototype device and machine learning algorithm's interpretation of the prototype device.

**Hypothesis 2A:**

The categorical classifications of tympanogram types based on audiologist's interpretation of the prototype device versus machine learning algorithm's interpretation of the prototype device are not significantly different.

**Objective 2B:**

To obtain preliminary estimates of the accuracy of the prototype device based on machine learning algorithm's interpretation compared to commercial tympanometer based on audiologist's interpretation.

**Hypothesis 2B:**

The diagnostic accuracy (sensitivity and specificity) of the prototype device based on machine learning algorithm's interpretation as compared to the commercial tympanometer based on audiologist's interpretation is 80% or greater.

**Objective 3 (secondary):**

To investigate the differences in numerical measures (ear canal volume, static admittance and tympanometric peak pressure) between the commercial and prototype devices.

**Hypothesis 3:**

There are no statistically significant differences in numerical measures (ear canal volume, static admittance and tympanometric peak pressure) between the commercial and prototype devices.

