Analyses for the pilot validation will include: 1) comparison of categorical classifications of tympanogram types for the commercial vs prototype devices; 2) evaluating potential intra-participant correlation between ears; 3) assessing differences in numerical measures between the commercial and prototype tympanometer; and 4) evaluating performance of mHealth tympanometer and commercial tympanometer.

- 1) For each device, commercial and prototype, tympanograms will be categorized into one of 3 categories: A, B and C. To assess the agreement between the two devices with respect to categories, Bowker's test of symmetry and the Kappa coefficient conventional methods to assess agreement, will be used. For the initial analysis, both tympanograms will be performed for each ear and no adjustments will be made for participants (i.e., most will have both ears included).
- 2) To assess the potential effect of participant and ear status (normal, diseased) for participants where both ears are included, each participant's ears will be characterized as (both normal, both diseased, one diseased and one normal). Within those categories, the number of ears for which there is concordance between the two tympanograms for each participant will be 0, 1 or 2. Pearson's chi-square test will be used to compare the three groups defined by ear status with respect to the distributions of the number of ears with concordance.
- 3) The Wilcoxon signed rank test will be used to determine if the differences in the numerical measures (ear canal volume, static admittance and tympanometric peak pressure) obtained from the commercial and prototype devices are significantly different from zero. No adjustment for multiple testing is planned.
- 4) Audiologist assessment of the mHealth and commercial tympanometers will be captured through questionnaires which assess 4 performance measures using a 5-point Likert scale. For each performance measure, the Kappa coefficient and Bowker's test of symmetry will be used to assess agreement between the two mHealth and commercial tympanometers with respect to responses.

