**Hypothesis 4:**

There are no statistically significant differences between commercial device and prototype device ease of use.

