## 5 Analysis Plan

### 5.1 General Considerations

Analysis timeline: The final statistical analysis will be performed after study data is available from 30 participants (60 ears); and the Center for Hearing Health Equity data management team has completed the transfer of an analysis-ready dataset to the study statistician.

Statistical Software: The analysis will be done using SAS (version 9.4) and R (version 4.3.2). A two-sided alpha of 0.05 will be used to determine statistical significance.

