#### **5.4 Analysis of Secondary Endpoints**

**Comparison of ear canal volume (ECV), static admittance (SA) and tympanometric peak pressure (TPP):** The agreement in ECV, SA, and TPP between the commercial device and prototype device using Bland-Altman approach. The difference plot (plot of difference in measurement vs mean measurement) will be used to visualize the difference as well as to assess the assumption of normality for the differences. The limits of agreements (LoA) will be constructed: mean of difference  $\pm 1.96 \times \text{SD}$  of difference. It is expected that LoA will capture 95% of the differences in measurements between the two devices. The distributional assumptions related to Bland-Altman method will be validated (e.g. normality of difference will be tested for statistical significance using Shapiro-Wilk's test) and alternate approaches such as data transformation may be employed if needed. It is anticipated that the difference in ECV and TPP between the commercial device and prototype device will be within 0.4 and 40 measurement units respectively. The difference in distribution of the ECV, SA, and TPP will be assessed (separately) for statistical significance using Wilcoxon signed rank test.

**Comparison of ease of device usage:** The ease of device usage based on audiologist's assessment will be measured using a 4-question survey. Each survey question is presented on 5-point Likert scale (Completely Disagree, Disagree, Neither agree or disagree, Agree Completely, Agree). The response will be assigned a score of 1-5 (corresponding to Completely Disagree-Completely Agree) with higher score indicating greater

degree of agreement. For each audiologist an aggregated score will be obtained. The aggregated score will range from 4-20 with higher score suggesting greater ease of use. Each audiologist will contribute two assessments – one for the prototype device and the other for the commercial device. The difference in aggregated score between the two devices will be tested for statistical significance using Wilcoxon signed rank test.

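### Hypothesis 3 is worded so that a non-significant Wilcoxon test supports it, and it is not tied to the Bland-Altman analysis that the SAP itself plans for agreement

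*SAP*

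**What the plan says.** SAP 1.3 states Objective 3, a secondary objective, as "To investigate the differences in numerical measures (ear canal volume, static admittance and tympanometric peak pressure) between the commercial and prototype devices". The hypothesis attached to it is "There are no statistically significant differences in numerical measures (ear canal volume, static admittance and tympanometric peak pressure) between the commercial and prototype devices".

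SAP 5.4 plans two things for these measures. The first is Bland-Altman: difference plots, limits of agreement at the mean difference ± 1.96 SD, and a normality check. It adds an expectation that the differences in ear canal volume (ECV) and tympanometric peak pressure (TPP) "will be within 0.4 and 40 measurement units respectively". No value is given for static admittance (SA). The second is a test: the difference in distribution of each measure "will be assessed (separately) for statistical significance using Wilcoxon signed rank test". SAP 5.1 sets the level: "A two-sided alpha of 0.05 will be used to determine statistical significance".

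The Protocol, under Pilot Validation Analysis, names only the test for these measures: "The Wilcoxon signed rank test will be used to determine if the differences in the numerical measures" differ from zero. It does not mention limits of agreement.

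Two other SAP hypotheses have the same form. Hypothesis 2A says that the audiologist's and the algorithm's classifications "are not significantly different". Hypothesis 4 says "There are no statistically significant differences between commercial device and prototype device ease of use".

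**The concern.** The statement to be supported is a null hypothesis, with no margin and no power attached. Failure to reject it is not evidence that two devices agree. The signed rank test asks whether the differences are centred on zero. It does not ask how far apart the two readings are in an individual ear, which is what matters when one device is to stand in for another.

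Hypothesis 3 could therefore be reported as supported for an imprecise prototype whose errors happen to balance, and as not supported for a precise prototype with a small constant offset. The SAP says the study will guide design modifications, and the Protocol says it will support a grant application for a larger validation study. Either misreport could carry forward into those decisions.

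**Working it through.** **Inputs from the documents.** 60 ears from 30 participants (SAP 2.2 and 5.1); two-sided alpha 0.05 (SAP 5.1); limits of agreement = mean ± 1.96 SD, and anticipated differences of 0.4 for ECV and 40 for TPP (SAP 5.4).

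**Assumptions.** The documents give no bias, SD or between-ear correlation for these differences, so a range is shown. Differences are taken as normal. The 40 units serve only as a reference line.

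**The SAP's own figure.** The limits are expected to capture 95% of differences: 2Φ(1.96) − 1 = 0.9500. This reproduces for normal differences. No power or sample size is stated for Hypothesis 3.

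**What the test responds to.** For normal differences the chance of rejection depends on bias/SD and the number of ears. A large-sample approximation, using the Wilcoxon efficiency 3/π = 0.955, is Φ(√(60 × 0.955) × bias/SD − 1.96). Simulation (4,000 sets of 60 independent differences) gives:

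| TPP bias | SD | Limits of agreement | Ears beyond 40 | Test significant |
|---|---|---|---|---|
| 0 | 50 | −98 to +98 | 42% | about 5% |
| 0 | 80 | −157 to +157 | 62% | about 5% |
| 5 | 15 | −24 to +34 | about 1% | about 70% |
| 5 | 10 | −14.6 to +24.6 | under 0.1% | about 97% |
| 20 | 80 | −137 to +177 | 63% | about 46% |
| 40 | 80 | −117 to +197 | 66% | about 96% |

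- Row 1: limits 0 ± 1.96 × 50 = ±98. Share beyond 40 = 2 × (1 − Φ(40/50)) = 2 × (1 − 0.788) = 0.42. With no bias the rejection rate is alpha, whatever the SD.
- Row 4: bias/SD = 0.5, and Φ(7.57 × 0.5 − 1.96) = Φ(1.82) = 0.966, in line with the simulation.
- Row 6 also has bias/SD = 0.5, so the test treats it like row 4, although about two thirds of its ears lie beyond 40 and almost none do in row 4.

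ECV gives the same rejection rates when bias and SD are scaled to 0.4 instead of 40.

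**Two ears per person.** SAP 5.4 applies the test to ear-level differences without allowing for clustering; SAP 5.3 does allow for it in the primary analysis. At a between-ear correlation of 0.5 the variance of the mean is inflated by 1 + 0.5 = 1.5, so the effective critical value is 1.96/√1.5 = 1.60 and false rejection is 2 × (1 − Φ(1.60)) = 0.11. Simulation also gives about 11%.

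**Hypothesis 4.** SAP 5.4 has each audiologist contribute one assessment per device, and the Protocol expects about 3 audiologists at one site and 2 at the other. With 5 pairs the smallest two-sided exact signed rank p-value is 2/2⁵ = 2/32 = 0.0625. On that reading significance at 0.05 is impossible, even if all five favour the same device. SAP 2.1 has the questions answered after each participant, so the unit of analysis also needs stating.

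**A tempting remedy, checked.** Suppose the confidence limits of the limits of agreement had to lie inside ±40. For bias 5 and SD 15 the upper limit is 5 + 1.96 × 15 = 34.4. Its approximate standard error is 15 × √(3/60) = 3.35, and its upper 95% confidence limit is 34.4 + 2.00 × 3.35 = 41.1, outside 40. In simulation with independent ears such a device meets the rule only about 41% of the time.

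**The case against.** The strongest reply is that the SAP already has the right analysis. SAP 5.4 uses the word agreement for Bland-Altman and puts it first; Wilcoxon comes last. With SD 50, the planned output would show limits near ±98 beside an anticipated 40, and a careful reader would not be misled. The objective is worded as an investigation, is secondary, and belongs to a first-in-human pilot. This stands. It places the defect in the wording of the hypothesis and its missing link to the planned limits, not in the absence of an agreement analysis.

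A reader might infer that widely disagreeing devices would pass in general. They would not: the 95% applies when differences centre near zero and ears are independent. With bias equal to the anticipated limit and SD twice that limit, the test rejects about 96% of the time. With between-ear correlation 0.5, the 95% falls to about 89%.

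A reader might also infer that the SAP commits to declaring agreement from a non-significant test, or that 0.4 and 40 are acceptance limits. Neither is written. There is no pass/fail rule. The two values are only anticipated, the SAP does not say whether they refer to the mean difference or to individual ears, and SA has none.

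For Hypothesis 2A, SAP 5.3 already plans kappa with a cluster-bootstrap interval, so little has to change there.

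**Conclusion.** The point holds as one of wording and linkage. Taken literally, Hypothesis 3 can be settled only by a test that does not measure agreement. Under the assumed values, the test is non-significant about 95% of the time when 42% of ears differ by more than 40 units (no bias, SD 50), and significant about 97% of the time when almost none do (bias 5, SD 10). Ignoring the pairing of ears raises false rejection to about 11% at an assumed correlation of 0.5. The sizes depend on those assumptions and on normality. The insensitivity to spread at zero bias does not depend on the SD chosen.

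The documents do not support saying that agreement is left unanalysed or that any poor device would pass. The point does not touch enrolment, data collection or the estimates of sensitivity and specificity. It does change what may be concluded on Objective 3, and by the same reasoning on Hypotheses 2A and 4.

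**What to change.** - **Hypothesis 3.** Restate it as an estimation statement resting on the planned Bland-Altman analysis. For each measure report the mean difference and the 95% limits of agreement, with confidence intervals that allow for two ears per participant; a bootstrap resampling participants, as already planned for kappa, would serve.
- **Anticipated values.** Have the sponsor state, before data lock, whether 0.4 and 40 refer to the mean difference or to individual ears, and whether a value is set for SA. Then compare the estimated limits with them. Do not require the confidence limits of the limits of agreement to fall inside these values, because 60 ears were not sized for that.
- **Wilcoxon.** Keep it as a descriptive check for systematic shift.
- **Hypothesis 2A.** Rest it on the planned kappa and its cluster-bootstrap interval.
- **Hypothesis 4.** Report the paired difference in score with its interval, and state whether the unit is the audiologist or the participant visit.

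The cost is SAP wording, some interval calculations and a sponsor decision on the anticipated values. No new data are needed. The downside is that the results may show wider limits than anticipated.

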**Objective 4 (secondary):**

To compare audiologists' perceptions on ease of use between commercial and prototype devices based on the 4-item 5-point Likert scale survey from audiologists.

**Hypothesis 4:**

There are no statistically significant differences between commercial device and prototype device ease of use.

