Eligible patients will be invited to participate, and the consent form reviewed. Consented participants will receive their audiological services as scheduled, with the addition of prototype measurements to their appointment. The audiology appointment will include routine ear and hearing measures, such as otoscopy (visual ear exam) and pure tone

Title: "Pilot Validation of a Prototype Mobile Health Tympanometer"
PI: [name], MPH
Institution: University of Arkansas for Medical Sciences

testing. The prototype device will be conducted before the commercial tympanometry. Audiologists will be asked to complete the prototype measurement and interpretation prior to the commercial device to limit bias in study results. We anticipate approximately 3 audiologists from UAMS and 2 audiologists from AC being involved in the study. Audiologists will be provided initial training and a demonstration of the prototype device and given instruction on how to troubleshoot and who to contact should an unanticipated problem occur. The tympanometric measurement takes roughly 10-15 seconds per ear to collect. We anticipate the prototype measurement and data entry will take no more than 5 minutes to complete during the audiological appointment.

The resulting tympanograms from the prototype device and the clinical tympanometer will be interpreted by the audiologist and entered in a secure Research Electronic Data Capture (REDCap) database. The audiologist will also answer a few brief questions during/after testing each participant in a REDCap form on device performance for both the prototype and commercial tympanometers.

Specifically, the order of events will be as follows:

1. Audiologist will test each ear of the participant with the prototype device and interpret the tympanogram. These findings will be entered in a secure Research Electronic Data Capture (REDCap) database in real time using a tablet or computer.
2. Next, the audiologist will test each ear of the participant with a commercial tympanometer, interpret the results and enter them in the database as described above.
3. The audiologist will complete 4 questions on each device performance between testing with each device (steps 1 and 2) if time permits, or after completion of testing with both the devices, and document it in a secure REDCap database.

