## 2 Study Methods

### 2.1 Study Design

Pilot Validation: This is a pilot validation study involving a comparative investigation of a commercially available tympanometer with a minimal risk lay-friendly (mHealth) tympanometer prototype. The pilot validation will be conducted in consented adults and children presenting to the Audiology Clinics of UAMS and AC. The study will evaluate device performance compared to a commercial tympanometer in patients with various middle ear pathologies. Data acquired from the pilot validation will also be used with our machine learning algorithm to determine how well it works with prototype data and the if there will be a need for further refinement.

Eligible patients will be invited to participate, and the consent form reviewed. Consented participants will receive their audiological services as scheduled, with the addition of prototype measurements to their appointment. The audiology appointment will include routine ear and hearing measures, such as otoscopy (visual ear exam) and pure tone testing. The prototype device will be conducted before the commercial tympanometry. Audiologists will be asked to complete the prototype measurement and interpretation prior to the commercial device to limit bias in study results.

The resulting tympanograms from the prototype device and the clinical tympanometer will be interpreted by the audiologist and entered in a secure Research Electronic Data Capture (REDCap) database. The audiologist will also answer a few brief questions after testing each participant in a REDCap form on device performance for both the prototype and commercial tympanometers.

Specifically, the order of events will be as follows:

1. Audiologist will test each ear of the participant with the prototype device and interpret the tympanogram. These findings will be entered in a secure Research Electronic Data Capture (REDCap) database in real time using a tablet or computer.
2. Next, the audiologist will test each ear of the participant with a commercial tympanometer, interpret the results and enter them in the database as described above.
3. Finally, the audiologist will complete 4 questions on user experience with the prototype and commercial devices and document it in a secure REDCap database.

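### SAP Hypothesis 4 (ease of use) can be supported only by a non-significant test, with no interval for the paired difference; with about five audiologists an exact test could never contradict it

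*SAP*

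**What the plan says.** Objective 4 in SAP 1.3 is "To compare audiologists' perceptions on ease of use between commercial and prototype devices", a secondary objective. Its hypothesis reads "There are no statistically significant differences between commercial device and prototype device ease of use".

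SAP 5.4 sums the four Likert items: "The aggregated score will range from 4-20 with higher score suggesting greater ease of use". The named analysis is: "The difference in aggregated score between the two devices will be tested for statistical significance using Wilcoxon signed rank test". SAP 5.1 sets the threshold: "A two-sided alpha of 0.05 will be used to determine statistical significance".

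Neither document gives a confidence interval for the paired difference, a margin or a power figure for this endpoint. SAP 2.2 sizes the study on the precision of sensitivity and specificity only. SAP 5.4 does state anticipated differences for ear canal volume (0.4) and tympanometric peak pressure (40), but none for ease of use.

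The unit of analysis is described in two ways. SAP 5.4 says "For each audiologist an aggregated score will be obtained", with two assessments per audiologist, one for each device. SAP 2.1 says "The audiologist will also answer a few brief questions after testing each participant", which would give about 30 pairs. On the number of raters, the Protocol (Study Design and Procedures) says: "We anticipate approximately 3 audiologists from UAMS and 2 audiologists from AC being involved in the study".

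**The concern.** The hypothesis is itself a statement about significance, so p > 0.05 is the only outcome that agrees with it. Whether p exceeds 0.05 depends on the number of pairs and the spread of the scores as much as on the device. With few pairs, non-significance is likely even if the prototype is harder to use. The test also has no direction, so a prototype rated clearly easier would count against the hypothesis whenever the test is able to reject.

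SAP 1.1 says the results will guide design changes before large-scale validation. For that, the team needs the size, direction and uncertainty of any usability gap. A p-value read against Hypothesis 4 gives none of these.

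**Working it through.** There is no planned figure to reproduce, because neither document states power or precision for ease of use.

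**Inputs from the documents.** Score range 4 to 20; paired signed rank test; two-sided alpha 0.05 (SAP 5.1, 5.4). About 3 + 2 = 5 audiologists (Protocol). About 30 participants (SAP 2.2).

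**Assumed inputs.** The SD of the paired difference is not given; 2, 3 and 4 points are used. True differences of 1 and 2 points are used for illustration.

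**Case 1: one pair per audiologist (SAP 5.4), n = 5.**
- Under the null hypothesis the 2^n sign patterns are equally likely, so the smallest exact two-sided p is 2/2^n. For n = 5 this is 2/32 = 0.0625, above 0.05. For n = 6 it is 2/64 = 0.031.
- With five audiologists the exact test cannot reject in either direction. At least six non-zero differences, all of one sign, are needed.
- Normal approximation, all five differences of one sign and no ties: W = 15, mean 5 × 6/4 = 7.5, variance 5 × 6 × 11/24 = 13.75. Then z = 7.5/3.708 = 2.02 and p = 0.043. With a continuity correction, z = 7.0/3.708 = 1.89 and p = 0.059.
- The SAP does not say exact or approximate, so the same five ratings could fall on either side of 0.05 by choice of software option.

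**Case 2: one pair per visit (SAP 2.1), n = 30, treated as independent.** Signed rank test simulated with normal differences rounded to whole points and zeros dropped. Chance of a non-significant result:

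| True deficit | SD 2 | SD 3 | SD 4 |
|---|---|---|---|
| 1 point | 28% | 59% | 75% |
| 2 points | 0% | 7% | 28% |

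Repeat simulations move these by a point or two. The test is symmetric, so an advantage of the same size would contradict Hypothesis 4 with the complementary chance; for 2 points at SD 3 this is 100% − 7% = 93%.

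Independence is the favourable assumption. Thirty visits over five audiologists is about six ratings each, and ratings by one person are likely to resemble each other.

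**What an interval would show.** 95% half-width = t(0.975, n − 1) × SD/√n.
- n = 5, SD 3: 2.776 × 3/2.236 = 3.7 points (2.5 at SD 2, 5.0 at SD 4).
- n = 30, SD 3, independent: 2.045 × 3/5.477 = 1.1 points (0.75 at SD 2, 1.5 at SD 4).

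The scale is 16 points wide.

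**The case against.** The strongest reply is that no sentence in either document says equality will be declared when p > 0.05. Objective 4 is only to compare, SAP 5.4 says only that the difference will be tested, and Hypothesis 4 can be read as a clumsily written null hypothesis. That is right about the text: a reader might infer a rule that concludes equal ease of use, and the documents contain no such rule. What stands is that the hypothesis as worded can be supported only by non-significance, and no interval is planned to qualify that result.

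A reader might also infer that a harder prototype would often pass and an easier one would fail. The documents do not support that as a general statement. With five audiologists and an exact test, an easier prototype cannot contradict the hypothesis at all. With 30 independent pairs, a 2-point deficit is missed only 0% to 28% of the time; frequent misses are confined to smaller differences or a large SD.

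It would also be too strong to say that no estimate is planned. SAP 5.2 gives means with SDs and medians with interquartile ranges for continuous variables, which would cover the two device scores, and a mean difference follows from complete pairs. The interval for that difference is what is missing.

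Finally, this is a secondary endpoint in a pilot, SAP 1.1 allows justified deviations, and Hypotheses 2A and 3 use similar wording. These points limit the priority of the change but do not make non-significance informative.

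**Conclusion.** The point holds as a defect in how Hypothesis 4 is framed and reported. Under the unit stated in SAP 5.4, with about five audiologists and an exact test, the hypothesis is met whatever the ratings; a normal approximation could change that, which the SAP leaves open. Under the per-visit unit implied by SAP 2.1, a 1-point deficit is missed about 28% to 75% of the time and a 2-point deficit about 0% to 28%. In that case a clearly easier prototype would also contradict the hypothesis.

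The n = 5 bound follows from the anticipated number of audiologists. The n = 30 figures rest on assumed SDs of 2 to 4 points and on independent pairs. The change is worth making because it is nearly free, but it concerns a secondary endpoint and does not touch the primary analysis.

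**What to change.** 1. In SAP 1.3, replace Hypothesis 4 with an estimation aim, for example: *The paired difference (prototype minus commercial) in the 4-20 ease-of-use score will be estimated with a 95% confidence interval.*
2. In SAP 5.4, make that estimate and interval the reported result. Keep the signed rank p-value as supplementary, say whether it is exact or approximate, and state that p > 0.05 is not evidence of equal ease of use.
3. State one unit of analysis, consistently in SAP 2.1 and 5.4. If visits are the unit, the interval must account for repeated ratings by the same audiologist.
4. While editing, reconcile SAP 5.4 with the Protocol's Data Analysis section, which plans kappa and Bowker's test item by item for the same questionnaire.

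A margin is needed only if the team wants to claim that the prototype is not worse. The team would then have to set and justify it before data transfer. Objective 4 as written does not require one.

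The cost is a few sentences in the SAP and one interval, with no new data. The drawback is that the result may have to be reported as inconclusive, most clearly with five pairs, where the half-width is about 3.7 points at an assumed SD of 3.
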